**Participant recruitment:** 

Participation in this study will be exclusively on a volunteer basis. Every eligible participant

will receive a printed material containing information about the study and an written Informed

Consent formular in Croatian language will be obtained from every subject willing to participate

in the study. Participants will be divided in two groups: a) patients being diagnosed with

congestive heart failure (NYHA II-IV) and b) healthy volunteers (matched controls).

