# Prospective case-controlled study - CATSTAT-HF Conducted at the University Hospital of Split **Exclusion criteria** Pool of available participants for **Inclusion criteria** the study Non-probabilistic sampling Study inclusion/exclusion Total N of participants = 120 Prospective consecutive enrollment in 3:1 fashion (HF patients: healthy volunteers) Study start: Jan 2018 90 patients with documented heart failure Healthy volunteers (matched controls) (Total left ventricular ejection fraction spectrum Total N= 30 including LVEF <40%, 40-49%, ≥50 %) Measurements 1. Basic anthropometric parameters 1. Making of individual electronic and paper record for each 2. Clinical parameters of each enrolled participant participant (medical history and physical examination) 2. Noting the loss to follow-up 3. Transthoracic echocardiography 3. Noting the attrition rate and basic hemodynamic parameters 4. Peripheral blood drawing and respective laboratory analysis Study end: Jan 2019 Statistical and data analysis

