CATSTAT-HF

Official Title of the study:

Serum Catestatin Expression and Cardiometabolic Parameters in Patients With

Congestive Heart Failure (CATSTAT-HF)

NCT number:

NCT03389386

Date of the document:

April 15th 2019

Study organizations:

University of Split School of Medicine University Hospital of Split

STUDY ANALYSIS PLAN (SAP)

All data analyses will be performed by using IBM SPSS Statistics for Windows, version 23.0 (IBM Corp., Armonk, NY, USA) and/or Graphpad Prism 7 for Windows (GraphPad Software, Inc., La Jolla, CA, USA). All p-values in this study will be 2-tailed and results that reach p<0.05 will be considered statistically significant.

GENERAL STATISTICAL ANALYSES:

- 1. Descriptive analyses will provide data on particular categories of interest by using frequencies and percentages. Baseline sociodemographic, anthropometric and comorbidity burden data will be provided for each particular category.
- 2. A standard **Pearson's chi-squared test** will be used to determine statistical differences in categorical variables between the two groups of interest congestive heart failure-CHF patients vs. healthy volunteer controls and other potential subgroups of interest.
- 3. The unpaired **t-test** or **Mann-Whitney U-test**, based on the data distribution normality, will be used to determine statistical differences in continuous parameters between the two groups of interest *CHF patients vs. healthy volunteer controls* and other potential subgroups of interest, as needed. Continuous variables will be expressed as mean ± standard deviation (SD) or median ± interquartile range (IQR), based on the normality distribution.
- 4. **Bivariate Pearson correlation test (r)** is a parametric test that will be used to determine the significance of linear correlation between two continuous variables of interest (X, Y). In the determination of statistical correlation between continuous variables, a **multiple linear regression**, adjusted for confounders, will be used.

SPECIFIC STATISTICAL ANALYSES:

1. The analysis of variance (ANOVA) with post-hoc Tukey HSD test will be used to

determine statistical differences in continuous parameters among the three or more

subgroups of patients with CHF.

2. Receiver operating characteristics (ROC) curve analysis will be used to ascertain the

diagnostic sensitivity and specificity as well as corresponding cut-off values of serum

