catestatin in determining heart failure (HF) degree and severity, e.g. rule out, rule in.

3. All multivariable regression analyses will be, at minimum, adjusted for age, sex, estimated

glomerular filtration rate (eGFR), and body mass index (BMI). Other important factors such as

medication intake and other potential confounding factors will be used in determining odds

ratios (OR) for the disease status (congestive heart failure). Adjusted ORs, statistical

significance (p) and 95% confidence intervals (95% CI) will be provided for independent

predictors.

Study statistical plan is provided and revised on

April 15th 2019 by

[name], BSc

[contact]

12-

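### The SAP's ROC item mixes a severity aim with a diagnostic one and names no classes; with only healthy volunteers as non-HF subjects, the data cannot support a rule-in or rule-out cut-off for suspected heart failure.

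*SAP*

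**What the plan says.** The SAP, Specific statistical analyses, item 2, plans ROC curves. Their output is described as "diagnostic sensitivity and specificity as well as corresponding cut-off values of serum"; the sentence then gives the use of the marker as "catestatin in determining heart failure (HF) degree and severity, e.g. rule out, rule in". It does not name the positive and negative classes, the reference that defines them, the set of participants analysed, or any limit on how the cut-off may be used.

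The Protocol, Participant recruitment, defines two groups: "congestive heart failure (NYHA II-IV) and b) healthy volunteers (matched controls". The flow chart describes a "Prospective case-controlled study - CATSTAT-HF" with "Total N of participants = 120" and "Prospective consecutive enrollment in 3:1 fashion (HF patients: healthy volunteers", giving 90 patients with documented HF and 30 healthy volunteers. It states that sampling is non-probabilistic and that the HF group covers all bands of left ventricular ejection fraction (LVEF). NYHA class is among the clinical variables recorded for HF patients (Protocol, Procedures).

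**The concern.** A rule-in or rule-out cut-off is meant for people in whom HF is suspected. Its specificity has to come from those among them who turn out not to have HF, and many of these will have symptoms or illnesses of other kinds. This study has no such group. If the ROC compares HF with no HF, all the specificity information comes from 30 healthy volunteers. That tells us how well catestatin separates known HF from health, which is a different and usually easier question.

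Because item 2 allows either comparison, the study could follow its SAP exactly and still publish a diagnostic cut-off that its sample cannot support. Recruiting more people of the same two kinds, or validating the cut-off in them, would not cure this.

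**Working it through.** **1. The plan's own figure.** 120 × 3/4 = 90 and 120 × 1/4 = 30, so the flow chart's 3:1 split reproduces. The documents give no AUC, sensitivity, specificity, power, effect size or catestatin SD, so there is no accuracy figure to check.

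**2. The two readings of item 2.**

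- *Severity.* Degree and severity are the stated target, and item 1, just before, compares subgroups of CHF patients. On this reading the ROC sits within the 90 HF patients and the volunteers play no part.
- *Diagnosis.* The output is called diagnostic and the examples given are rule-out and rule-in. The SAP's main two-group contrast is CHF versus healthy volunteers, and item 3 models CHF as a disease status. Item 1 restricts itself to CHF patients; item 2 does not.

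The text does not decide between them. The control group matters to this point only on the second reading.

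**3. What the control group could do to accuracy (illustration).** Assume normal distributions with equal SD. HF lies *d* SD from healthy, in either direction. Symptomatic people without HF lie a fraction *f* of the way from healthy to HF. Neither *d* nor *f* is in the documents.

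AUC = Φ(d(1 − f)/√2). The column f = 0 is what a study with healthy controls would see.

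| d | f = −0.25 | f = 0 | f = 0.25 | f = 0.5 | f = 0.75 |
|---|---|---|---|---|---|
| 0.5 | 0.671 | 0.638 | 0.605 | 0.570 | 0.535 |
| 1.0 | 0.812 | 0.760 | 0.702 | 0.638 | 0.570 |
| 1.5 | 0.908 | 0.856 | 0.787 | 0.702 | 0.605 |
| 2.0 | 0.961 | 0.921 | 0.856 | 0.760 | 0.638 |

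For f from 0.25 to 0.75, the AUC against healthy controls is too high by 0.638 − 0.605 = 0.03 at the least and 0.921 − 0.638 = 0.28 at the most. At f = 0 there is no error. At f = −0.25 and d = 1.0 the healthy-control AUC is too low by 0.812 − 0.760 = 0.05.

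Specificity at the cut-off that gives 90% sensitivity (also an assumed target) is Φ(d − 1.282 − d·f). For d = 1.0:

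- f = −0.25: 0.49
- f = 0: 0.39
- f = 0.25: 0.30
- f = 0.5: 0.22
- f = 0.75: 0.15

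**4. Precision of a HF-versus-healthy ROC.** Specificity would rest on 30 people. As an example, 24/30 = 0.80 has a 95% Wilson interval of 0.63 to 0.91. For an AUC of A = 0.76 with 90 and 30 people, the Hanley-McNeil variance is [A(1 − A) + 89(u − A²) + 29(v − A²)]/(90 × 30), where u = A/(2 − A) = 0.613, v = 2A²/(1 + A) = 0.656 and A² = 0.578. The SE is 0.046, and the 95% half-width is 1.96 × 0.046 = 0.09.

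**The case against.** The strongest reply is that the sentence names degree and severity as its target, so the ROC was always meant for HF patients and the healthy volunteers are beside the point. This is a fair reading, and on it the control-group problem disappears. It does not remove the need for a change, because the item neither restricts the analysis to HF patients nor states a severity reference, and it still offers rule-out and rule-in as its examples.

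A second reply is that comparing cases with healthy controls is an ordinary early step for a biomarker. That also stands, and is why an exploratory HF-versus-healthy ROC need not be banned.

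The controls are also called matched. The matching factors are not given, and matching does not supply people with suspected HF.

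Four stronger inferences are tempting but go beyond the documents:

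- *Accuracy will be overstated.* This requires symptomatic non-HF patients to have catestatin levels nearer to HF than healthy people do. It is the expected direction, but no values are given, and a shift of zero or away from HF would remove or reverse the effect.
- *The study compares the two extremes of disease.* The HF group includes NYHA II and the whole LVEF range. The limitation lies on the control side.
- *The controls have no comorbidity.* The content of the eligibility criteria is not visible in the text available. Only the absence of a suspected-HF group is established.
- *The 3:1 ratio distorts predictive values.* The SAP does not promise predictive values, and sensitivity and specificity do not depend on the ratio as such.

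**Conclusion.** The point holds in a limited form. What the documents show is that item 2 has two purposes, leaves its classes undefined, and makes a diagnostic claim for which the study has no suitable comparison group. That conclusion needs no assumption about catestatin levels.

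Optimism in the AUC and specificity is an expectation, conditional on the ROC being run as HF versus healthy and on f being above zero. Its size in this study is unknown; the 0.03 to 0.28 range describes only the assumed model. The issue concerns one secondary analysis and the claim drawn from it, not the CHF-versus-healthy comparison of catestatin levels itself. It should be corrected before results are reported.

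**What to change.** Reword SAP specific item 2 as follows.

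- (a) Run the severity ROC in the 90 HF patients only, excluding the controls. State the severity reference in advance, for example NYHA III-IV versus II, which is already collected.
- (b) Report any CHF-versus-healthy ROC as exploratory discrimination from healthy subjects, with confidence intervals. Label any cut-off from it as not for diagnostic use.
- (c) Delete the rule-out, rule-in phrase.

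This costs SAP wording only and needs no new patients or measurements. Adding a suspected-HF group is not realistic: the SAP is dated April 15th 2019, after the flow chart's January 2019 study end and in the month the protocol's opening details give as the anticipated end. The downside is a less favourable headline accuracy claim, and a severity ROC that uses 90 people instead of 120. The precision of that ROC cannot be stated now because the documents do not give the expected split by NYHA class.
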